1.2.4. Study Procedures

The schedule of assessments, as outlined in the study protocol, is provided in Table 1-2.

Table 1-2 Schedule of Events

	Visit 1	Visit 2	Visit 3	Visit 4	Visit 5	Visit 6	Visit 7	Visit 8	Visit 9
Visit # and Timing	204 1	Б 1	5 4	Day 4	Day 8	Day 15	Day 29	Day 85	Day 181
	-28to -1	Day 1	Day 2	± 1 day	± 1 days	± 2 days	± 2 days	±7 days	±7 days
Informed consent ¹	X						-	_	
Inclusion/exclusion	X	Review							
Demographics ²	X								
Medical history	X								
Vital signs ³	X	$X \times 2^3$	X	X	X	X	X	X	X
Physical exam	X	X^4	X^4	X^4	X^4	X^4	X	X^4	X^4
TEAEs, SAEs, MAAEs, AESIs ⁵	X	$X \times 2$	X	X	X	X	X		
Concomitant medications ⁵	X	$X \times 2$	X	X	X	X	X		
Pregnancy test ⁶	X	X					X		
Screening for HIV, HCV, HepB (5 mL) ⁷	X								
Rapid antigen test for SARS-CoV-2		X							
Hematology, chemistry, and coags (10.7 mL) ⁸	X	X		X	X		X		
HLA-B27 Testing		X							
Urinalysis ⁹	X			X	X		X		
MARV antibody tests (2 x 10 mL) ¹⁰		X			X	X	X	X	X
Blood for research (100 mL) ¹¹								X	
PBMC/T-cell Assay ¹²		X			X		X		
Transcriptomics (2.5mL PaxGene RNA tube) ¹³		$X \times 2$	X	X	X	X			
MARV viremia (7 mL) and shedding ¹⁴		$X \times 2$	X	X	X	X	X		
Cytokine levels (10mL) ¹⁵		X		X	X		X		
Vaccination		X							
Post-vaccination observation ¹⁶		X							
Provision of emergency contact card		X							
Training and review of Memory Aid		X	X	X	X	X	X	X	X

Abbreviations: AESI = Adverse Event of Special Interest; eCRF = electronic case report form; HBsAg = hepatitis B surface antigen; HCG = human chorionic gonadotropin; Hct = hematocrit; HCV = hepatitis C; HepB = hepatitis B; HgB = hemoglobin; HIV = human immunodeficiency virus; INR = international normalized ratio; MAAE =

medically attended adverse event; RBC = red blood cell; PBMC = peripheral blood mononuclear cell; PCR = polymerase chain reaction; PT = prothrombin time; PTT = partial thromboplastin time; SAE = serious adverse event; TEAE = treatment emergent adverse event; WBC = white blood cell.

Footnotes:

- ¹ Obtain written informed consent for participation in the clinical study, clinical samples, and HIV testing.
- ² Demographic data include age, height and weight (for BMI), race, and ethnicity.
- ³ Vital signs will include blood pressure and pulse while seated and at rest, and body temperature measured orally. On Visit 2, vital signs will be assessed up to 60 minutes before vaccination, then at 60-90 minutes after vaccination and at 6h ± 1h. (Shown as X × 2)
- ⁴ Directed physical examination at discretion of Investigator. See the Protocol for the Arthritis Pathway algorithm for subjects with joint complaints. If rash is present on any visit, the PI should reference the Dermatology Pathway.
- ⁵ SAEs, MAAEs, and AESIs will be recorded from day of consent until EOS. AEs will be recorded beginning with Screening. All TEAEs will be recorded from dosing on day 1 through day 29, and during the rest of the study. Concomitant medications will be recorded up to 6 months prior to study entry and throughout the duration of the study. This will include dietary supplements and other prophylactic substances.
- ⁶ Pregnancy tests (serum HCG) will be done in all female subjects at Screening. Repeat pregnancy tests (urine) will be done in all female subjects prior to vaccination and at day 29.
- ⁷ Screening serology will include HIV-1, HIV-2, HCV, and HBsAg.
- ⁸ Clinical laboratory assessments will include CBC (HgB, Hct, RBC, platelets), WBC with differential, metabolic chemistry panel, PT, PTT, and INR.
- ⁹ Urinalysis assessments by dipstick. Reflex testing by microscopy for abnormal blood or leukocyte esterase.
- ¹⁰ Two 10 mL tubes for serology: minimum of 6 (1.5 mL) aliquots of serum frozen. Four tubes will be used for viremia and neutralization studies and two tubes will be preserved at baseline and held for possible AE assessment. Collect one 10 mL tube for Rheumatologic or Dermatologic baseline
- 11 Blood collection for serology and purification of IgG (100 mL). 10×10 mL SST tubes to be centrifuged, then the serum should be split as 10 mL aliquots in each of 5 x 15 mL conical sterile tubes and frozen at -60°C.
- 12 Collect 6 \times 10 mL EDTA tubes for PBMC separation and cryopreservation.
- ¹³ Collect in 2.5 mL PaxGene RNA tube for transcriptomics before dosing, then at 6h (± 1h) and on each subsequent visit as indicated.
- ¹⁴ Blood (7 mL) for plasma, saliva (swab) and urine sample for virus detection before dosing, then at 6h (± 1h) and on each subsequent visit as indicated.
- ¹⁵ Blood (10 mL) for plasma cytokines, aliquoted into 4 × 1 mL cryotubes and frozen at -60°C.
- $^{16}\,\mathrm{Includes}$ TEAEs and examination of injection site 60-90 minutes after vaccination.

1.2.5. Safety and Immunogenicity Parameters

1.2.5.1. Safety Parameters

Safety will be assessed by analysis of the occurrence of treatment emergent adverse event (TEAE) and vaccine viremia, as well as by adverse changes in laboratory evaluations (chemistry, hematology, urinalysis, etc.), vital signs, and physical findings, including neurologic examinations. Solicited AEs will be collected systematically through Day 29; unsolicited TEAEs, medically attended adverse events (MAAEs), SAEs, and AESIs will be collected for the entire duration of a subject's participation in the study with the help of Memory Aids reviewed at every visit The primary safety endpoints are:

- Incidence and severity of solicited injection site AEs (arm pain, local tenderness, erythema (redness), induration (swelling/firmness) and systemic AEs (objective fever, subjective fever, chills, sweats, headache, myalgia, arthralgia, fatigue, nausea, vomiting) and neurological AEs (blurry vision, changes in balance or coordination, confusion, disorientation, dizziness, severe headache, shaking or body tremors, slurred speech, tingling or numbness, weakness or feeling weak) between Days 1 and 8, Days 9-15, and up to Day 29 after vaccination, per treatment group (active vaccination versus placebo).
- Incidence and severity of unsolicited AEs between Days 1-8, Days 9-15, and up to Day 29 after vaccination, per treatment group (active vaccination versus placebo) and stratified by relatedness, i.e., not related vs related.
- Incidence and severity of arthritis and skin/mucosal lesions up to Day 29 after vaccination using standard case definitions and stratified by relatedness. This includes where possible quantitative reverse transcription polymerase chain reaction (RT-qPCR) for detection of PHV01 and lesion biopsy for histopathology.
- Incidence of SAEs observed up to Day 181 and stratified by relatedness.
- Incidence and severity of MAAEs observed up to Day 181 and stratified by relatedness.
- Physical and neurological examination results, vital signs, normal and abnormal clinical laboratory values (hematology and clinical chemistry, urinalysis).
- Incidence of AESIs up to Day 181, including pneumonitis, acute respiratory distress syndrome, multiorgan failure, a hemorrhagic diathesis, certain neurologic events (encephalitis, myelitis, aseptic meningitis, optic neuritis, transverse myelitis, generalized convulsions, Guillain-Barré Syndrome, acute disseminated encephalomyelitis), thrombocytopenia, anaphylaxis, and vasculitides.

Secondary safety endpoints include the following:

• PHV01 in blood on Days 1 (at 0 and 6 hours), 2, 4, 8, 15, and 29, as detected by quantitative reverse transcription polymerase chain reaction (RT-qPCR)

- o Proportion of subjects with viremia detected by RT-qPCR
- Median duration of viremia, determined by RT-qPCR
- o Geometric mean level of viremia, geometric mean peak level of viremia, and area under the curve (AUC)
- PHV01 in urine, saliva, biopsy, joint fluid, vesicle fluid, or swab of other suspect lesions on Days 1 (at 0 and 6 hours), 2, 4, 8, 15, and 29, as detected by RT-qPCR
 - o Proportion of subjects with PHV01 detected by RT-qPCR
 - o Median duration of PHV01, determined by RT-qPCR
 - Geometric mean copy number of PHV01, geometric mean peak copy of PHV01, and AUC

1.2.5.2. Immunogenicity Parameters

The primary immunogenicity endpoints are as follows:

- Geometric mean titers (GMT) of Marburg GP protein-specific IgG antibody as measured by ELISA on Days 1 and 29
- GMT of PsVNT₅₀ and PsVNT₈₀ MARV GP-specific neutralizing antibody titers (the reciprocals of the serum dilutions at which 50% and 80% of the input pseudovirion was neutralized, respectively) as measured by Pseudovirion neutralization assay (PsVNA) on Days 1 and 29

If the corresponding titer value is below the lower limit of quantitation (LLOQ), the titer value will be considered as LLOQ/2 at such visit for GMT computation. For ELISA titers below limit of detection (LOD), the titer will be assigned a value of 1 ELISA unit/mL for GMT computations.

Secondary immunogenicity endpoints include the following:

- GMT Marburg GP protein-specific IgG ELISA antibody on all other study days through Day 181
- GMT PsVNT₅₀ and PsVNT₈₀ on all other study days to Day 181
- Seroconversion rate defined as at least 4-fold increase in Marburg GP-specific IgG (ELISA) titer compared to Day 1 for subjects with baseline titers > LLOQ. Otherwise, if baseline titer < LLOQ or <LOD, seroconversion is defined as at least 4-fold increase over LLOQ/2.
- Seroconversion rate defined as at least 4-fold increase in Marburg GP-specific neutralizing antibody titer PsVNA compared to Day 1 for subjects with baseline titers > LLOQ.

Otherwise, if baseline titer < LLOQ, seroconversion is defined as at least 4-fold increase over LLOQ/2.

- Geometric mean fold increase in Marburg GP-specific IgG (ELISA)
- Geometric mean fold increase in Marburg GP-specific neutralizing antibody titer (PsVNA)
- Seroresponse rate defined as at least 2-fold increase in Marburg GP-specific IgG (ELISA) compared to Day 1 for subjects with baseline titers > LLOQ. Otherwise, if baseline titer < LLOQ or <LOD, seroresponse is defined as at least 2-fold increase over LLOQ/2.
- Seroresponse rate defined as at least 2-fold increase in Marburg GP-specific neutralizing antibody titer PsVNA compared to Day 1 for subjects with baseline titers > LLOQ.
 Otherwise, if baseline titer < LLOQ, seroresponse is defined as at least 2-fold increase over LLOQ/2.
- Reverse cumulative distribution of titers (IgG ELISA and PsVNA)
- The correlation between the IgG ELISA and neutralizing antibody titers on all study days tested
- The correlation between blood viremia AUC and IgG ELISA and neutralizing antibody

Exploratory immunogenicity endpoints include the following:

- Wild-type Marburg neutralization against one or more Marburg lineages
- Marburg ELISA against one or more Marburg lineages
- Determination of Fc-mediated cell-targeting vaccine-specific antibodies, e.g., ADCC, ADNP, ADMP, etc.
- Vaccine-specific T-cell responses to Marburg GP protein by intracellular cytokine staining (ICS) and/or enzyme-linked immune absorbent spot (ELISPOT)
- Determination of Marburg IgM ELISA antibody responses
- Determination of vaccine-specific pro-inflammatory markers, such as CRP, ICAM-1, VCAM-1 levels, and cytokine levels
- Determination of vaccine-specific gene activation by RNA transcript sequencing (transcriptomics)
- Determination of B or T cell responses to VSV proteins

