3.10. Missing, Unused, and Spurious Data

In general, there will be no substitutions made to accommodate missing data points. All data recorded on the case report form will be included in data listings that will accompany the CSR.

Subjects with negative post-baseline antibody response (defined as the corresponding titers < LLOQ) will have a titer value assigned as LLOQ/2.

When tabulating AE data, partial dates will be handled as follows. If the day of the month is missing, the onset day will be set to the first day of the month unless it is the same month and year as study treatment. In this case, in order to conservatively report the event as treatment-emergent, the onset date will be assumed to be the date of treatment. If the onset day and month are both missing, the day and month will be assumed to be January 1, unless the event occurred in the same year as the study treatment. In this case, the event onset will be coded to the day of treatment in order to conservatively report the event as treatment-emergent. A missing onset date will be coded as the day of treatment.

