Additionally, Analysis of Variance (ANOVA) models will be used to compare each PHV01 dose level to one another and to placebo for Days 8 (if tested), 15, 29, 85 and 181. The response variable will be the log-2 transformed ELISA titer values for the time point under consideration. If there is a significant difference between the GMTs, i.e., where the p-value from the F-test is < 0.05, then post-hoc pairwise tests using Tukey's method will be used to compare each dose with one another and each dose with placebo. The estimated mean differences on the log-2 scale between the treatment groups will be expressed as the ratio of GMTs. The base-2 antilogarithm of each mean difference represents the GMT ratio and the base-2 antilogarithms of the 95% CI limits for the mean difference represent the confidence limits for the GMT ratio.

Similarly, the mean fold increase of ELISA titers and PsVNT will be calculated by subtracting the base-2 log transformed values at baseline (Day 1) from the respective study day (Day 8 [if tested], 15, 29, 85, 181) for each subject and averaged within treatment group. If baseline titer value is <LLOQ or <LOD (ELISA only), baseline will be assigned as LLOQ/2 for purposes of deriving fold increase. The results will be presented by transforming back the anti-log. The 95% CI will be calculated based on the inverse of the log2 transformed fold increase values from the t-distribution. Results will be presented for each study day (Day 8 [if tested], 15, 29, 85, 181) by treatment group along with a combined PHV01 group, and the descriptive statistics will include the geometric mean fold-increase from baseline, the geometric standard deviation, 25th percentile, median, 75th percentile, minimum, and maximum values.

Pairwise ratios of the geometric mean fold rise and the associated 95% confidence intervals will be estimated for each PHV01 dose group relative to one another and to the placebo group, as well as the ratio of the combined PHV01 dose group relative to the placebo group on Days 8 (if tested), 15, 29, 85, and 181. Pairwise comparisons will be performed using Satterthwaite's t-test. T-tests will be performed on log-2 transformed values of the individual fold-rise values. The resulting estimated mean difference and associated 95% CI will then be back transformed using base-2 antilogarithms to obtain estimates on the ratio scale.

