4.3.2. Seroconversion Rate and Distribution of ELISA Titers and PsVNT

Seroconversion is defined as at least 4-fold increase in the titer when compared to baseline (Day 1). If the baseline titer is <LLOQ or <LOD (ELISA only), the baseline value used to determine seroconversion will be assigned as LLOQ/2. In these cases, seroconversion occurs if the fold-increase at post-baseline visit is greater than or equal to 4 times the LLOQ/2.

The seroconversion rate of ELISA titers and PsVNT and their exact 95% CIs based on the Clopper-Pearson method will be presented by treatment group and combined PHV01 group on Days 8 (if tested), 15, 29, 85, 181. The comparison between each of the PHV01 vaccine dose levels, the combined PHV01 vaccine group, and the placebo arm will also be performed. Comparisons will be based on the 95% CI for differences in seroconversion rate and will use the Newcombe score method. The analysis will be repeated separately for males and females. These

differences will be used to indicate possible dose-related responses. A difference in seroconversion rate between a given PHV01 dose group and placebo that is greater than zero (i.e., if the lower bound of the 95% CI for difference in seroconversion rate is greater than zero) indicates the rate of seroconversion in the PHV01 dose group is larger than the rate in the placebo group.

Reverse cumulative distribution curves of ELISA titers and PsVNT will be generated by treatment group on Days 8 (if tested), 15, 29, 85, 181 respectively, where the x-axis will be the observed log-2 transformed titers and the y-axis will be the percentage of subjects having a log-2 transformed titer greater than or equal to each of the observed log-2 transformed titers on the x-axis.

Boxplots by study day and treatment group will present the mean, median, interquartile range, and 95% CI for the ELISA titers and PsVNT levels on the log-2 scale and will be overlaid with jittered dots representing individual datapoints. Spaghetti plots will also be plotted for ELISA titers and PsVNT levels on log-2 scale by days since dosing, treatment group and subject. Line plots will present GMTs for ELISA titers and PsVNT50 levels at each visit by treatment group.

Exploratory endpoints to examine aspects of both cell mediated and humoral immunity will be collected but not analyzed.

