8. REVISION HISTORY

8.1. Changes from Statistical Analysis Plan Version 1.0: 23 April 2024

Revisions were made to the SAP sections 1.2.5.2, 4.3, and 4.4.3 to reflect the handling of <LOD and <LLOQ results for immunogenicity and vaccine viremia analyses. The data handling rules were provided in the following memorandums from Battelle and PHV, respectively:

- Memo titled "Reporting of Test Sample Values, including LOD and LLOQ, for B06748 Data Transfer Files and Final Report Data Tables", dated 28 May 2024.
- Memo titled "PHV01-C-101 Translation of Test Sample Results and Definitions", dated 30 May 2024.

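### The SAP gives a Day 29 ELISA titer below the LOD two conflicting values for the primary GMT, leaves its value in the fold increase unsettled, and misstates the seroconversion threshold in Section 4.3.2

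*SAP*

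**What the plan says.** The SAP handles low titers in several places.

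- **GMT, Section 1.2.5.2.** For a titer below the LLOQ, "the titer value will be considered as LLOQ/2 at such visit for GMT computation". ELISA results below the LOD are treated differently: "For ELISA titers below limit of detection (LOD), the titer will be assigned a value of 1 ELISA unit/mL for GMT computations". There is no such exception for PsVNT.
- **General data handling, Section 3.10.** "Subjects with negative post-baseline antibody response (defined as the corresponding titers < LLOQ) will have a titer value assigned as LLOQ/2". This sentence names no assay and no purpose, and it has no LOD exception.
- **Fold increase, Section 4.3.1.** "If baseline titer value is <LLOQ or <LOD (ELISA only), baseline will be assigned as LLOQ/2 for purposes of deriving fold increase". The section does not say what a post-baseline result below the LOD becomes.
- **Seroconversion, Section 4.3.2.** For a low baseline, "the baseline value used to determine seroconversion will be assigned as LLOQ/2", and then "seroconversion occurs if the fold-increase at post-baseline visit is greater than or equal to 4 times the LLOQ/2". Section 1.2.5.2 instead asks for a rise of at least 4-fold over LLOQ/2.
- **Revision history, Section 8.1.** "Revisions were made to the SAP sections 1.2.5.2, 4.3, and 4.4.3 to reflect the handling of <LOD and <LLOQ results". Section 3.10 is not in that list.

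ELISA GMT on Days 1 and 29 is a primary immunogenicity endpoint (1.2.5.2). Section 3.2 plans formal tests on it, and Section 4.3.1 specifies Satterthwaite t-tests on log titers. Neither LOD nor LLOQ appears in the documents, and the two memos cited in Section 8.1 for these rules are not included.

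**The concern.** A result below the LOD is also below the LLOQ, so 1.2.5.2 and 3.10 both apply to the same Day 29 ELISA value and give different numbers. Two programmers who each follow the SAP could report different primary GMTs, GMT ratios, confidence intervals and p-values.

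The matter would be minor if few results fell below the LOD. But Protocol Section 4.5 excludes people with prior VSV infection, a VSV-vectored or filovirus vaccine, or potential filovirus contact. Many placebo results, and most baseline results, may therefore be below the LOD. That is an inference; the documents do not state it. If it is right, the substitution rule largely sets the placebo GMT, which is the denominator of every comparison with placebo. The Day 29 interim analysis in SAP 3.12, which is meant to guide dose selection for the next trial, reports these ELISA results.

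The fold increase has a related gap, and the literal seroconversion criterion in 4.3.2 is not the one in 1.2.5.2.

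**Working it through.** **Inputs.** Group sizes are 10 per dose and 6 placebo; planning GMT is 1400 EU/mL and geometric SD 3.3, both from a related Ebola vaccine; detectable ratios are 6.4-fold (80% power) and 8.6-fold (90%) (all SAP 3.1). LLOQ = L is assumed between 2 and 100 EU/mL because the documents give none.

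**The plan's own figure.** Two-sided equal-variance t-test on ln titers, SD = ln 3.3 = 1.194, 14 df. At 6.4-fold the noncentrality is 1.856 / (1.194 × √(1/10 + 1/6)) = 3.01, and power is 79.9%. At 8.6-fold it is 90.0%. Pooled (30 vs 6), power is 80.4% at 4.7-fold and 89.8% at 5.9-fold. The figures reproduce. They assume geometric SD 3.3 with no floor, so the conflict does not change them.

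**1. GMT ratio.** Let p_P and p_V be the shares below the LOD in placebo and vaccine. Replacing LLOQ/2 by 1 lowers each log mean by p × ln(L/2), so

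ratio (floor 1) = ratio (floor L/2) × (L/2)^(p_P − p_V).

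| LLOQ (EU/mL) | p_P − p_V = 1 | p_P − p_V = 0.5 |
|---|---|---|
| 2 | 1.0 | 1.0 |
| 5 | 2.5 | 1.6 |
| 10 | 5 | 2.2 |
| 50 | 25 | 5.0 |
| 100 | 50 | 7.1 |

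Equal shares give a factor of 1. The step from 1 to L/2 equals the 6.4-fold detectable ratio at L = 2 × 6.4 = 12.8 EU/mL. With a vaccine GMT of 1400 and all placebo below the LOD, the ratio is 1400 with floor 1, and 280, 56 or 28 with LLOQ/2 at L = 10, 50 or 100.

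**2. Effect on the test.** Suppose all placebo subjects and 5 of 10 vaccinees are below the LOD, and the other 5 vaccinees lie between LOD and LLOQ. Under 1.2.5.2 the vaccine log values are 0 (five) and s = ln(L/2) (five). The mean is 0.5s, the SD √(2.5s²/9) = 0.527s, and the standard error 0.527s/√10 = 0.167s. So t = 3.0 on 9 df and p = 0.015 for any L above 2, with GMT ratios of 2.2, 5.0 or 7.1 at L = 10, 50 or 100. Under 3.10 all 16 values equal L/2 and the ratio is exactly 1. The shift from undetectable to detectable may be real, but the rule alone sets its size.

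**3. Day 1 against Day 29.** Section 3.10 covers post-baseline results only. If it governs Day 29 while 1.2.5.2 governs Day 1, a group below the LOD at both visits has a GMT of 1 on Day 1 and L/2 on Day 29: an apparent 25-fold rise at L = 50 with no change in any result.

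**4. Fold increase.** For a subject below the LOD at both visits, the baseline is L/2 by 4.3.1. If 3.10 supplies the later value, the fold is (L/2)/(L/2) = 1. If 1 is carried over from the GMT rule, it is 1/(L/2) = 2/L: 0.20, 0.04 or 0.02 at L = 10, 50 or 100.

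**5. Seroconversion with a low baseline.** Section 1.2.5.2 requires a titer of at least 4 × L/2 = 2L. Read literally, 4.3.2 requires a fold of at least 2L over a baseline of L/2, which is a titer of 2L × L/2 = L². At L = 50 that is 2500 against 100 EU/mL. A subject at the planning GMT, 1400/25 = 56-fold, would fail the literal 100-fold criterion. The opening sentence of 4.3.2 itself says at least 4-fold over baseline.

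**The case against.** The best defence is that the rules are labelled by purpose: 1 EU/mL for GMTs, and LLOQ/2 as the baseline for fold increase. On that reading 3.10 is the general rule and 1.2.5.2 an exception for ELISA GMTs, and 3.10 then supplies the sensible post-baseline value for fold increase. This is reasonable, but the SAP does not say it. Section 3.10 has no carve-out, and Section 8.1 suggests that it was not revisited when the LOD rules were added.

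Part of the defence stands against stronger readings that a reader might infer:

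- **That the GMT and fold-increase baseline rules contradict each other.** They have different stated purposes. Their results need not agree (1400 against 56 at LLOQ 50 when all baselines are below the LOD), but the textual conflict is between 1.2.5.2 and 3.10.
- **That the floor of 1 inflates the ratio.** This holds only relative to LLOQ/2, with LLOQ above 2 and a larger share below the LOD in placebo. The true titers are unknown. If the LOD is below LLOQ/2, then LLOQ/2 gives undetectable samples a value above the LOD and may understate the ratio.
- **That the floor of 1 weakens the dose comparisons.** This is not shown. Take one of 10 vaccinees below the LOD, the others at GMT 1400 and geometric SD 3.3, placebo all at the floor, and LLOQ 50. The geometric SD is about 12.8 with floor 1 and 5.5 with floor 25, but t against placebo is 8.1 and 6.7. Comparisons between doses were not computed.

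PsVNT GMTs have no 1-unit rule. Seroconversion and seroresponse use LLOQ/2 as the low baseline, and the rank-based Wilcoxon option in 4.3.1 and the medians depend less on the floor. Section 3.1 also says that the sample size was not set for formal hypothesis testing, although 3.2 plans such tests.

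**Conclusion.** The concern holds in three parts. First, a Day 29 ELISA result below the LOD has two prescribed values for the primary GMT and its tests. Second, its value in the fold increase is settled only if 3.10 governs; otherwise a subject below the LOD at both visits scores 2/LLOQ instead of 1. Third, 4.3.2 compares a ratio with a titer and conflicts with 1.2.5.2; that sentence covers both assays.

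The conflict and the wording error rest on the text alone. The size does not. The factor of 1 to 50 on the GMT ratio assumes LLOQ between 2 and 100 EU/mL and the extreme split of all placebo and no vaccinees below the LOD, and it shrinks to 1 as the shares converge. A reader might infer a 10- to 50-fold bias, but that needs an LLOQ of 20 to 100 as well as that split, and it treats LLOQ/2 as the truth. The documents support neither. The floor conflict does not affect PsVNT or the stated power figures. Fold increase and seroconversion are secondary endpoints.

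**What to change.** Before any analysis by treatment group, so that the choice cannot depend on the results:

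1. State one ELISA rule for results below the LOD and below the LLOQ, by visit and purpose, and align 3.10 with 1.2.5.2 and 4.3. LLOQ/2 throughout is the simplest choice, because 3.10, 4.3.1 and 4.3.2 already use it. It is a convention and has not been shown to be the correct value.
2. Report the primary GMT ratio with the other floor as a labelled sensitivity analysis.
3. Use the same floor at baseline and post-baseline for fold increase.
4. Correct 4.3.2 so that, for a low baseline, seroconversion means a post-baseline titer of at least 4 × (LLOQ/2).
5. State LOD and LLOQ, and report the number of results below each by group and visit.

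The cost is SAP wording and one derivation. If LLOQ/2 is chosen, the GMT ratio over placebo may become less favourable than under the 1 EU/mL rule.
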